The above mentioned use cases entail that the CGM data are accurate. Therefore, the first part of this research proposal is to investigate whether the newest state-of-the-art CGM devices used in Novo Nordisk trials are in fact accurate. Based on these results, it is investigated to which degree glycaemic variability can be revealed.

Short lay summary of the proposed research intended for public disclosure

Use of devices for continuous monitoring of the blood sugar is valuable for people with diabetes to understand their disease and to help prevent low blood sugar. Furthermore, continuous monitoring should be used in drug development to evaluate efficacy and safety. However, the devices have been criticised for being too inaccurate. This investigation sought to reveal the inaccuracies of current devices and to assess the subsequent usability related to the mentioned use cases.

Research methodology and data (brief description of the intended method for the use of the requested data and a detailed description of the different data sources of the data that is intended to be included)

To investigate the accuracy of CGM, mean absolute relative difference (MARD) will be calculated and presented and the impact of the delay assessed by time shifting CGM measurements. Furthermore, correlation analyses, between for example, PG and first derivative of IG, will be performed to try to understand when CGM devices tend to measure inaccurate. Lastly, machine learning and/or deep learning approaches will be utilised to reveal glycaemic patterns and to detect/predict outcomes, such as, hypoglycaemia.

Different glycaemic variability investigations will be undertaken:

- Test of PG vs IG and effect on clinical research. [analysis of differences]
- Correlation between PG values at bedtime and nocturnal hypoglycaemic events [correlation analyses]
- Effect of main evening meal and meal-time dose on nocturnal hypoglycaemic events [correlation analyses]
- Prediction of PG-confirmed hypoglycaemic events with CGM, dose and meal data as input [machine learning]
- The optimal dose and meal distribution and least CGM variability / eHbA1c [machine learning]
- Algorithm to suggest optimal dosing in relation to glycaemic variability [machine learning]

Requested data are demographic, CGM, meal, dose and hypoglycaemia data from the following trial. The analyses are independent of treatment and therefore the treatment arm can be blinded.

NN1218-3854

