APPENDIX 1: ANALYSIS PLAN

More of the investigation are of an exploratory and descriptive nature without use of treatment arm and the below information is therefore not always feasible to provide.

Endpoints: Difference between PG and IG. Number of Level 1 and 2 CGM hypoglycaemic events. Time in range of CGM and PG values. Sensitivity and specificity of different models.

Analysis Set: In an intention-to-“participate” manner all non-missing data will be used in these investigations. Imputation of missing values will in some cases be necessary, see below.

Statistical models: Difference analysis will be carried out using 2-sample t-tests or more advanced models such as ANOVA or MMRM with adjustment of sex, BMI, geographical region etc. where applicable. Machine learning approaches will include models such as Kernel SVM and neural networks with PCA, SEPCOR and forward selection for feature elimination.

Transformation of data: Transformations of data will be necessary to “fit” data into the machine learning models. For example, this will include splitting up data in training and evaluation data. If data are not normally distributed, logarithmic transformation may in most cases be performed.

Handling of missing data: Multiple imputation will be used when applicable, but for signal imputation, simpler methods will be used. For example, to get pairs of CGM and glucose meter data, linear interpolation of “missing” CGM data at the time points of glucose meter data may be applied.

Multiplicity issues: For multiple hypotheses testing simple Bonferroni corrections will be made to control the type 1 errors when applicable.

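### Holm's step-down procedure could replace single-step Bonferroni at the same family-wise error level: an efficiency gain, not the correction of an error

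*SAP*

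**What the plan says.** The whole multiplicity plan is one sentence in SAP Appendix 1. It says that, when several hypotheses are tested, "simple Bonferroni corrections will be made to control the type 1 errors", and it closes with the qualifier that this is done where applicable. Single-step Bonferroni is the only procedure named. The closing qualifier governs whether a correction is made, not which one. Neither document gives a reason for the choice, such as a wish for simultaneous confidence intervals.

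The tests that could be corrected are described loosely. On methods the SAP says: "Difference analysis will be carried out using 2-sample t-tests or more advanced models such as ANOVA or MMRM". The endpoint list begins "Endpoints: Difference between PG and IG. Number of Level 1 and 2 CGM hypoglycaemic events. Time in range of CGM and PG values" and ends with the sensitivity and specificity of models. The Protocol's methodology section introduces its own list with "Different glycaemic variability investigations will be undertaken" and gives six items: one analysis of differences, two correlation analyses and three machine learning items.

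No alpha, family of hypotheses, number of tests, sample size or power is stated. The SAP also says of itself: "More of the investigation are of an exploratory and descriptive nature without use of treatment arm", and that "the below information is therefore not always feasible to provide".

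**The concern.** Single-step Bonferroni compares every p-value with alpha/m, however many hypotheses have already been rejected. Holm relaxes the threshold after each rejection and keeps the same family-wise guarantee. It works from the same p-values and needs no independence assumption. That matters here, because glucose differences, hypoglycaemic event counts and time in range in the same participants are likely to be correlated.

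What is at stake is power. Wherever the SAP's commitment to type 1 error control applies to two or more tests, a real effect with a p-value between the Bonferroni threshold and the relevant Holm threshold could be reported as non-significant although the promised error control did not require it. In largely exploratory work, a missed association is a relevant cost.

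**Working it through.** The plan gives no figure to reproduce. The check has two parts: an argument that needs no numbers, and an illustration on assumed inputs.

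**1. Why Holm loses nothing.** Order the p-values p(1) ≤ … ≤ p(m).
- Bonferroni rejects each hypothesis with p ≤ alpha/m.
- Holm compares p(1) with alpha/m, p(2) with alpha/(m−1), and so on up to p(m) with alpha, and stops at the first failure.

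The first threshold is the same in both and every later Holm threshold is larger. Anything that Bonferroni rejects, Holm therefore rejects too. Both control the family-wise error strongly under any dependence.

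**2. Assumed inputs (none is in the documents).** Two-sided family-wise alpha 0.05; unadjusted power 80% per test; z-tests; m from 2 to 10; independent tests, with a correlation of 0.5 as a variation.

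**3. Bonferroni power per test.** The mean of the test statistic is 1.960 + 0.842 = 2.802. Power is Φ(2.802 − z), where z is the 1 − alpha/(2m) quantile.
- m = 2: z = 2.241, Φ(0.560) = 71.2%
- m = 6: z = 2.638, Φ(0.163) = 56.5%

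**4. Holm by hand for m = 2, both nulls false, independent tests.** Let b = 0.712 (power at 0.025) and a = 0.800 (power at 0.05).
- Average power: b + (a − b)b = 0.712 + 0.088 × 0.712 = 0.775
- Power to reject both: a² − (a − b)² = 0.640 − 0.008 = 0.632, against b² = 0.507 for Bonferroni

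**5. Larger m, by simulation (200,000 replicates per scenario), independent tests, all nulls false.**

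| m | Average power, Bonferroni | Average power, Holm | Gain (points) |
|---|---|---|---|
| 2 | 71.1% | 77.4% | 6.3 |
| 3 | 65.9% | 75.1% | 9.2 |
| 4 | 61.9% | 72.6% | 10.7 |
| 6 | 56.5% | 68.3% | 11.8 |
| 10 | 49.8% | 60.9% | 11.1 |

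The m = 2 row agrees with the hand calculation to within simulation error.

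**6. Less favourable cases (same assumptions).**
- Half the nulls false: a gain of 2.6 points at m = 4 (61.8% to 64.4%) and 3.2 points at m = 6 (56.5% to 59.6%, before rounding 56.45% to 59.63%).
- One null false: about 0.1 to 0.2 points.
- m = 1: the two procedures are identical.
- Correlation 0.5, all nulls false: gains of 5.2 (m = 2), 9.1 (m = 4), 10.3 (m = 6) and 10.9 points (m = 10).
- Probability of at least one correct rejection: the same when all nulls are false, and less than 0.3 points apart otherwise.

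**7. Error control.** With all nulls true, the two procedures had the same family-wise error. In mixed scenarios Holm used more of the allowance (for example 0.037 against 0.025 with three of six nulls false, independent tests) but never exceeded 0.048.

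**The case against.** The strongest reply is that this is a preference: Bonferroni controls the error it is meant to control, much of the work is exploratory, a correction is promised only where applicable, and no treatment comparison depends on it. That stands as a limit on severity. It does not remove the point, because wherever the SAP does correct, Holm gives the same error bound and at least as many rejections.

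A reader might infer from the Protocol's six items that six tests form the family, and take the m = 6 row as the loss in this study. The documents do not support that. Three of the items are machine learning with no stated hypothesis test, one item need not be one test, and the number of tests is nowhere given. The m = 6 row also assumes that every null is false, which is the favourable case.

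A reader might also wish to apply Holm separately within each investigation. That would be a different change. The SAP does not define its family. If it meant to correct across all tests, separate families each at 0.05 would loosen control: with independent families the overall error could reach 1 − 0.95³ = 14% for three, or 1 − 0.95⁶ = 26% for six. With one test per investigation it would also make m = 1, where Holm gains nothing.

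Finally, Holm is not wholly without a drawback. Bonferroni yields simple simultaneous confidence intervals and Holm does not readily do so. This has some weight for an estimation endpoint such as the difference between plasma and interstitial glucose, although the SAP neither plans such intervals nor cites them as a reason.

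**Conclusion.** The point holds as an optional efficiency improvement. That Holm rejects at least as much as Bonferroni at the same family-wise level is certain, and depends on no assumption about this study.

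The size of the gain is not certain. Under the assumed alpha, power and independence, it runs from nothing (m = 1) through 0.1 to 0.2 points (one false null) and about 3 points (half false, m = 4 to 6) to about 6 points (m = 2) or 12 points (m = 6) when all nulls are false. These figures are illustrations. They should not be read as the power lost in this study.

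Two stronger readings are not supported. One is that the SAP's correction is wrong: it is valid. The other is that real associations will be missed because of it: the documents give no effect size, sample size or count of tests from which that could be shown.

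**What to change.** In SAP Appendix 1, Multiplicity issues, replace the single-step Bonferroni wording with *Holm step-down adjusted p-values*, applied to the same family of tests and at the same family-wise alpha that Bonferroni would have used. Do not narrow the family to each investigation as part of this change.

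The sentence should also list the hypotheses in the family and state the alpha, since neither procedure can be applied until both are known. That gap exists whichever method is kept.

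The cost is one sentence in the SAP and one software option, with no new data. If simultaneous intervals are wanted, Bonferroni-adjusted intervals can be reported beside the Holm p-values. A note should then say that the two may disagree where Holm rejects and Bonferroni does not.
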